9.1.3. Study Halting Rules

Section 11.6 of the protocol provides criteria that would trigger an immediate halt to dosing for all subjects until an assessment by the study team has taken place, and an amendment is submitted to, and approved by, the competent authority. Both solicited and unsolicited adverse events, and which (if any) study halting criteria they meet, are collected on the Study Halting Rule CRF, and will be presented in a data listing.

9.2. Clinical Laboratory Evaluations

The following tests will be performed by the local laboratory:

- Hematology:
 - White Blood Cells (WBC) Count
 - Hemoglobin (Hb)
 - Platelets (PLT)
 - Absolute Neutrophils
 - Absolute Lymphocytes
 - Absolute Monocytes
 - Absolute Eosinophils
 - Absolute Basophils
- Chemistry:
 - Alkaline phosphatase (ALP)

- Alanine aminotransferase (ALT)
- Aspartate aminotransferase (AST)
- Total bilirubin
- Creatine kinase (C)
- Serum creatinine
- Coagulation:
 - Prothrombin Time (PT)/INR
 - Activated Partial Thromboplastin Time (aPTT)
- Serology:
 - HIV
 - Hepatitis B Surface Antigen (HbsAg)
 - Hepatitis C Antibody (HCV Ab)
 - SARS-CoV-2 serology (N-specific)

Serum or urine pregnancy test - Cohort 6 only: women of childbearing potential must have a negative urine or serum pregnancy test at screening for eligibility purposes and within 24 hours prior to each study vaccination. No tables but a listing will be provided for the test. Clinical safety laboratory parameters evaluated after receipt of GRT-R910 will include WBC, Hb, PLT, ALT, AST, ALP, total bilirubin, CK, and creatinine.

Actual results and changes from baseline values for hematology and serum chemistry tests will be summarized by study days and treatment group for scheduled visits only.

A summary of toxicity grades (from 0 to 4 where 0 is Normal result (not included in the other grades), 1 is Mild, 2 is Moderate, 3 is Severe, 4 is Potentially Life-threatening) will be reported by study days and treatment group using the frequency count and percentage of subjects in each category. Toxicity grading will be performed according to FDA guidance for healthy subjects [7]. For chemistry and hematology parameters, shift in toxicity grades from baseline will be summarized by study days and treatment group using the frequency count and percentage of subjects in each category. The shift in toxicity grades will be from baseline to the worst-case post-vaccination, which will include unscheduled and repeated assessments, will also be presented. If the toxicity grade is missing for an existing lab value, then it will not be imputed, and the result will be summarized in the “Grade Missing” category. Missing grades will not be included in the overall denominator of toxicity grade summaries.

Subjects will be screened for HIV, hepatitis B surface antigen, antibody to hepatitis C virus and SARS-CoV-2. Results will be discussed with the subject. If a positive result occurs, the subject will be referred for appropriate follow-up and results will be reported as required by state law. These screening tests must be negative for the subject to be eligible to participate. Serology data will not be summarized.

For subject with Early Termination (ET) visit, the ET visit will be set to the next protocol scheduled visit following ET within the specific study period. If the subjects completed all the scheduled visits and then discontinued, no mapping will be done. The worst-case toxicity grades post-vaccination, which will include unscheduled assessments, will also be presented.

All laboratory data will be presented in a data listing.

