3.2 Schedules of Assessments

Table 1 Schedule of Assessments: Cohorts 1 and 2 – Subjects NOT Receiving Booster Dose

Study Visit	V00	V01	V02	V03	V04	V05	V06	V07	V08	Unsch Visit	Early Term Visit
Study Day(s)	SCR -30 to -1	Day 1	Day 2 +1d	Day 4 +2d	Day 8 +2d	Day 29 ±3d	Day 57 ±3d	Day 180 ±3d	Day 365 ±7d		
Obtain Written Informed Consent	X										
Review Eligibility Criteria	X	X									
Medical History	X										
Review of Interim Medical History		X	X	X	X	X	X	X	X	X	X
Concomitant Medications	X	X	X	X	X	X	X	X	X	X	X
Vital Signs (Oral Temp, Pulse, BP)	X	X			X	X	X	X	X	X	X
Physical Examination Including Height and Weight	X										
Targeted Physical Examination, if Indicated		X			X	X	X	X	X	X	X
Nasal Swab Collection for SARS-CoV-2 PCR	X										X ⁷
Blood Collection for Safety Labs	X ¹				X ²		X ²	X ²		X ²	X ²
Blood Collection for HBsAg, Anti-HCV, SARS-CoV-2 Serology ³ , HIV	X						X ³				
Blood Collection for Cellular Immune Assays		X			X	X		X	X	X	X
Blood Collection for Antibody Assays		X				X	X	X	X	X	X
Vaccination		X									
45 Minute Evaluation After Study Vaccination		X									
Distribute Memory Aid and Study-Related Materials		X									
Review Memory Aid			X	X	X					X ⁴	X ⁴

Study Visit	V00	V01	V02	V03	V04	V05	V06	V07	V08	Unsch Visit	Early Term Visit
Study Day(s)	SCR -30 to -1	Day 1	Day 2 +1d	Day 4 +2d	Day 8 +2d	Day 29 ±3d	Day 57 ±3d	Day 180 ±3d	Day 365 ±7d		
Adverse Events		X	X	X	X	X				X ⁵	X ⁵
SAEs/AESIs Including PIMMCs/MAAEs/NOCMCs ⁸		X ⁹	X	X	X	X	X	X	X	X	X
Phone Visit ⁶			X	X							
Saliva Collection for Antibodies		X			X			X			

Abbreviations: AESI, adverse event of special interest; BP, blood pressure; HBsAg, hepatitis B surface antigen; HCV, hepatitis C virus; HIV, human immunodeficiency virus; MAAE, Medically Attended Adverse Event; NOCMC, New Onset Chronic Medical Condition; SAE, serious adverse event; PCR, polymerase chain reaction; PIMMC, Potentially Immune-Mediated Medical Condition; SARS-CoV-2, severe acute respiratory syndrome coronavirus 2; SCR, screening; Unsch, unscheduled

- Includes white blood cells (WBCs), hemoglobin (Hb), platelets (PLT), alanine aminotransferase (ALT), aspartate aminotransferase (AST), alkaline phosphatase (ALP), total bilirubin, creatine kinase (CK), serum creatinine, prothrombin time (PT)/international normalized ratio (INR), and activated partial thromboplastin time (aPTT)
- Includes WBCs, Hb, PLT, ALT, AST, ALP, total bilirubin, CK, and serum creatinine
- Includes SARS-CoV-2 serology (N-specific) only

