8.1. Efficacy analysis

COVID-19 incidence in subjects will be assessed using two separate metrics. The number and percentage of subjects who had (1) a positive nasal swab SARS-CoV-2 PCR test during the study and (2) an Adverse Event with a MedDRA preferred term of "COVID-19", "Asymptomatic COVID-19", or "COVID-19 pneumonia" will be summarized for the SAF.

For both measures, the incidence rate (IR) is defined as the number of subjects with an event divided by the number of subjects at risk and person-days adjusted by person-years (total time at risk). The IR's of subjects with (1) positive PCR and (2) MedDRA preferred terms indicating COVID-19 will be reported in the fashion of 100 person-years (see the [formula below](#)).

$$IR = \frac{\text{number of subjects with positive PCR}}{\text{sum(Person - days at risk)}} * 365.25 * 100$$

Person-Days at risk are defined as the total time from injection date of prime dose to the date of the positive PCR test for (1) or AE start date for (2), last date of study participation, data cutoff date, whichever is the earliest. The respective 95% CIs of positive nasal swab SARS-CoV-2 PCR tests and COVID-19-related adverse events will be calculated using the Clopper-Pearson [6] method.

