9.1.1.4. Adverse Events of Special Interest (AESI)

For this study, protocol specified AESIs are serologically or virologically confirmed SARS-CoV-2 infection or severe COVID-19. AESIs also include the Brighton Collaboration AESIs relevant to vaccination that are listed below:

- NOCMCs – defined as any new ICD diagnosis (per current International Statistical Classification of Diseases and Related Health Problems) that is applied to the subject during the course of the study, after receipt of the study agent, that is expected to continue for at least 3 months and requires continued health care intervention.
- MAAEs – defined as hospitalization, an emergency room visit or an otherwise unscheduled visit to or from medical personnel for any reason.
- PIMMCs – These constitute a group of AEs that includes diseases which are clearly autoimmune in etiology and other inflammatory and/or neurologic disorders which may or may not have autoimmune etiology. PIMMCs that are of special interest for this study are Brighton Collaboration AESIs relevant to vaccination that include: seizures, Guillain-Barre syndrome, acute disseminated encephalomyelitis, vasculitis, anaphylaxis, vaccine associated enhanced respiratory disease, thrombocytopenia, and thrombotic events.

All AESIs will be assessed, recorded, and followed as described above under AEs.

AESIs that meet SAE criteria will be reported on a SAE form within 24 hours of the site's awareness to the Gritstone/PPD Pharmacovigilance Group. In addition, for documentation and medical assessment purposes, AESIs that do not meet SAE criteria will also be reported on an SAE form within the period for AE reporting to the Gritstone/PPD Pharmacovigilance Group; however, the narrative will indicate that the AESI did not meet SAE criteria.

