- 7 A nasal swab for SARS-CoV-2 should be performed within 3 days of COVID-19 symptoms and repeated after 7 days.
- 8 AESIs, including serologically or virologically confirmed SARS-CoV-2 infection and severity of COVID-19, PIMMCs, MAAEs, and NOCMCs will be collected from the time of first vaccination throughout the entire study.
- 9 SAEs occurring after signing of the informed consent form (ICF) will be recorded and reported to the sponsor or designee by the investigator within 24 hours of becoming aware of the SAE.

Gritstone bio, Inc.
GO-009Statistical Analysis Plan, Version 5.0
Date Issued: 09JUN2023**Table 7 Schedule of Study Procedures: Cohorts 1 and 2 – Subjects receiving booster dose**

Study Visit	V00	V01	V02	V03	V04	V05	V06	V07	V08	V09	V10	V11	V12	V13	V14	Unsch Visit	Early Term Visit
Study Day(s)	SCR -30 to -1	Day 1	Day 2 +1d	Day 4 +2d	Day 8 +2d	Day 29 ±3d	Day 57 ±3d	Day 113 ¹² -3d/+21d	Day 114 +1d	Day 116 +2d	Day 120 +2d	Day 142 ±3d	Day 170 ±3d	Day 293 ±3d	Day 478 ±7d		
Obtain Written Informed Consent	X																
Review Eligibility Criteria	X	X						X									
Medical History	X																
Review of Interim Medical History		X	X	X	X	X	X	X	X	X	X	X	X	X	X	X	X
Concomitant Medications	X	X	X	X	X	X	X	X	X	X	X	X	X	X	X	X	X
Vital Signs (Oral Temp, Pulse, BP)	X	X			X	X	X	X			X	X	X	X	X	X	X
Physical Examination including Height and Weight	X																
Targeted Physical Examination, if indicated		X			X	X	X	X			X	X	X	X	X	X	X
ECG ⁸		X ⁹			X	X	X	X ⁹			X	X	X	X	X		
Cardiac Biomarkers (Troponin T, CRP, ESR) ¹⁰		X ¹¹			X	X	X	X ¹¹			X	X	X	X	X		
Nasal Swab Collection for SARS-CoV-2 PCR	X															X ⁷	
Blood Collection for Safety Labs	X ¹				X ²		X ²			X ²		X ²	X ²			X ²	X ²
Blood Collection for HBsAg, Anti-HCV, SARS-CoV-2 serology ³ , HIV	X						X ³						X ³				

Gritstone bio, Inc.
GO-009Statistical Analysis Plan, Version 5.0
Date Issued: 09JUN2023

Study Visit	V00	V01	V02	V03	V04	V05	V06	V07	V08	V09	V10	V11	V12	V13	V14	Unsch Visit	Early Term Visit
Study Day(s)	SCR -30 to -1	Day 1	Day 2 +1d	Day 4 +2d	Day 8 +2d	Day 29 ±3d	Day 57 ±3d	Day 113 ¹² -3d/+21d	Day 114 +1d	Day 116 +2d	Day 120 +2d	Day 142 ±3d	Day 170 ±3d	Day 293 ±3d	Day 478 ±7d		
Blood Collection for Cellular Immune Assays		X			X	X		X				X		X	X	X	X
Blood Collection for Antibody Assays		X				X	X	X				X		X	X	X	X
Vaccination		X						X									
45 Minute Evaluation After Study Vaccination		X						X									
Distribute Memory Aid and Study-Related Materials		X						X									

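### COVID-19 incidence in SAP 8.1 makes no use of the scheduled N-serology, so infection without symptoms is counted only if a site reports the positive result as an adverse event

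*SAP*

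**What the plan says.** SAP 8.1 defines two incidence measures. The first is "The number and percentage of subjects who had (1) a positive nasal swab SARS-CoV-2 PCR test during the study". The second is an adverse event coded to any of three MedDRA preferred terms, one of which is the term for asymptomatic COVID-19. Time at risk runs from the prime dose to the PCR date or AE start date, last participation or data cutoff, whichever comes first. A serology result does not enter either numerator, and a seroconversion date does not end time at risk.

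After screening, no swab is tied to a scheduled visit. The schedule footnote (SAP Appendix 1, Table 6, footnote 7; the same in Protocol 3.2) reads "A nasal swab for SARS-CoV-2 should be performed within 3 days of COVID-19 symptoms and repeated after 7 days".

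SARS-CoV-2 serology is drawn at screening and again after dosing. The later draw carries the footnote "Includes SARS-CoV-2 serology (N-specific) only" (Protocol 3.2). SAP 9.2 lists N-specific serology under its Serology heading and then states "Serology data will not be summarized". The same section puts all laboratory data in a listing.

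SAP 9.1.1.4 says that "protocol specified AESIs are serologically or virologically confirmed SARS-CoV-2 infection or severe COVID-19". This AESI has its own line in the whole-study summary of SAP 9.1.1 and its own planned output, Table 14.3.1.22. AESI occurrence is part of a primary endpoint (Protocol 3.1; SAP 2).

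**The concern.** The trial schedules a blood test that can show infection without symptoms, and names serologically confirmed infection as an AESI. The plan then keeps the result of that test out of every summary. Between a positive N result and a count in a table stands one step that the documents do not specify. Nothing defines seroconversion, says who turns a positive draw into an AESI, or gives the preferred term under which it is coded. Nothing requires Table 14.3.1.22 to agree with the laboratory data.

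At stake is the completeness of two descriptive results: the incidence in 8.1, and one AESI category within a primary safety endpoint. With 10 subjects per cohort, a single case is 10 percentage points.

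**Working it through.** **1. No figure to reproduce.** The documents state no expected infection rate, asymptomatic share, event count or power for COVID-19 incidence.

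**2. Follow one infection without symptoms that turns the N assay positive.**

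| Output | Is it counted? |
|---|---|
| SAP 8.1, PCR measure | No: without symptoms no swab is triggered |
| SAP 8.1, AE-term measure | Only if reported as an AE and coded to one of the three terms |
| Table 14.3.1.22 (AESI) | Only if reported as an AESI |
| Laboratory summary tables | No: excluded by SAP 9.2; none of the 87 tables in SAP Appendix 2 summarizes serology |
| Laboratory listing | Yes |

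**3. Possible size of the loss in the PCR measure.** Let A be the attack rate over follow-up and s the share of infections without symptoms. Both are assumptions.

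Expected missed infections = 50 × A × s. 
Chance of at least one missed = 1 − (1 − A·s)^50.

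| A | s | Infections | Missed | Chance of at least one missed |
|---|---|---|---|---|
| 10% | 20% | 5 | 50 × 0.10 × 0.20 = 1.0 | 1 − 0.98^50 = 63.6% |
| 20% | 35% | 10 | 50 × 0.20 × 0.35 = 3.5 | 1 − 0.93^50 = 97.3% |
| 40% | 50% | 20 | 50 × 0.40 × 0.50 = 10.0 | 1 − 0.80^50, nearly 100% |

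The proportion missed is s itself, so these rows translate the assumption into counts and do not estimate a bias. They apply to the PCR measure only.

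**4. One case in a cohort of 10.** With 0/10 the estimate is 0% (exact 95% CI 0 to 30.8%). With 1/10 it is 10% (0.3 to 44.5%).

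**5. How much the serology could recover.** Last scheduled N draw divided by last scheduled visit, in nominal study days (SAP Appendix 1, Tables 6 to 8):

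| Group | Last N draw / last visit | Share of follow-up |
|---|---|---|
| Cohorts 1–2, no booster | 57/365 | 15.6% |
| Cohorts 1–2, booster (draws at Days 57 and 170) | 170/478 | 35.6% |
| Cohorts 3–4, if Visit 13 takes place | 209/394 | 53.0% |
| Cohort 6, and Cohorts 3–4 without Visit 13 | 209/209 | 100% |

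The Day 209 position is read from SAP Table 8 and should be confirmed against the source table. If infection risk is even over time and a draw detects every earlier infection, these shares are the most that serology can recover.

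**6. Baseline status.** Protocol 10.2.1 and SAP 9.2 require the screening tests, SARS-CoV-2 included, to be negative. Exclusion 3 in Protocol 7.2 excludes an N-positive person from Cohorts 3, 4 and 6 only when there was also a compatible respiratory illness in the previous 112 days. On that wording some N-positive subjects could enter. A seroconversion measure needs a known negative baseline, so these sections must be reconciled.

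**The case against.** The strongest defence is that the AESI is handled separately. Serologically confirmed infection must be collected and reported throughout the study (Protocol 11.1.5, 11.2 and 11.2.1). The SAP gives it a category and a table, and the AE-term measure in 8.1 includes asymptomatic COVID-19. A site that reports a positive N result will see it counted. The no-summary sentence closes a paragraph on screening tests, and every result is listed; with 10 subjects per cohort and one or two post-dose draws each, a reader can find each seroconversion. The incidence is a descriptive addition to an uncontrolled Phase 1 trial of 50 with no hypothesis test.

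Most of this stands, and it rules out three stronger readings:

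- A reader might infer that the AESI is undercounted. The documents do not show that. Reporting is mandatory, and an undercount arises only if a positive draw is not carried into the AE data.
- A reader might infer that all infections without symptoms are lost. That is true of the PCR measure alone.
- A reader might infer that the trial has no infection indicator for interpreting late immunogenicity. That analysis has its own SAP (SAP 1 and 8.2), which is not available here, and the serology data exist.

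Two things remain. The no-summary sentence does reach post-dose N-serology, because SAP 9.2 lists that test under Serology. And a duty to report a confirmed infection does not say which laboratory result confirms one. A listing leaves that judgement to each reader.

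**Conclusion.** The point holds as a gap in ascertainment. The PCR measure cannot see infection without symptoms. The AE-term measure and Table 14.3.1.22 see it only through a reporting step that has no stated rule, and the test that could close part of the gap is kept out of the summaries. The direction of the PCR bias is downward. For the other two outputs there is a risk of undercounting, not a demonstrated one.

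The size cannot be fixed from the documents. Over assumed attack rates of 10–40% and asymptomatic shares of 20–50%, symptom-triggered PCR would miss 1 to 10 infections in 50 subjects. Serology would recover part of that, unequally: its draws span from 15.6% of follow-up (Cohorts 1–2 without booster) to 100% (Cohort 6). This is a worthwhile low-cost improvement to a descriptive analysis, not a threat to the trial's main conclusions.

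**What to change.** 1. In SAP 9.2, restrict the no-summary sentence to HIV, HBsAg and HCV.
2. In SAP 8.1, add a third, descriptive measure: N-seroconversion, defined as negative at screening and positive at a scheduled post-dose draw, among subjects N-negative at baseline. Add a composite of positive PCR, AE term or seroconversion. Give both as proportions by cohort with exact 95% CIs.
3. State when a positive N result counts as the AESI and how it is coded, and check every positive against Table 14.3.1.22 before database lock.
4. Show baseline N-status by cohort, and reconcile Protocol 10.2.1 and SAP 9.2 with exclusion 3 in Protocol 7.2.
5. Footnote the table with the last N draw in each schedule, so that differences between cohorts are not read as differences in infection.
6. Confirm that the vaccine's T-cell-epitope cassette cannot itself turn the N assay positive; the documents do not address this.

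The cost is about one table and a few sentences, from samples already scheduled. There are two downsides. A seroconversion is dated only to the interval between draws, so it supports a proportion and not a person-time rate. Coverage also stays partial and differs by cohort.

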9.3. Vital Sign Measurements

Actual values and changes from baseline for vital sign data (oral temperature, systolic and diastolic blood pressure, and pulse rate) will be summarized by study days and treatment for subjects in the Safety Analysis Set. Changes from baseline to each scheduled post-baseline visit will be presented.

A summary of toxicity grades (from 0 to 4 where 0 is Normal result (not included in the other grades), 1 is Mild, 2 is Moderate, 3 is Severe, and 4 is Life-threatening or disabling [Subjects will only have temperature up to grade 4]) will be reported by study days and treatment group using the frequency count and percentage of subjects in each category (for more information see the “Guidance for Industry: Toxicity Grading Scale for Healthy Adult and Adolescent Volunteers Enrolled in Preventive Vaccine Clinical Trials” [\[7\]](#)). Shift in toxicity grades from baseline will be summarized by study days and treatment group using the frequency count and percentage of subjects in each category. The shift in toxicity grades will be from baseline to the worst-case post-vaccination, which will include unscheduled and repeated assessments, will also be presented. Missing grades will be displayed as counts, but will not be included in the overall denominator of toxicity grade summaries.

All vital sign measurements will be presented in a data listing.

9.4. Cardiac biomarker

Cardiac biomarker assessment will be performed for Cohort 1 and 2 receiving booster dose only, and Cohort 3, 4, and 6.

Cardiac biomarker assessments include troponin T (cTnT), C-reactive protein (CRP), and erythrocyte sedimentation rate (ESR). The biomarker assessments will be summarized as mean, SD, median, min, max, and mean of actual value and as mean, SD, median, min, and max of change from baseline. An interpretation by study days table will be summarized for the SAF.

For subject with Early Termination (ET) visit, the ET visit will be set to the next protocol scheduled visit following ET within the specific study period. If the subjects completed all the scheduled visits and then discontinued, no mapping will be done.

All data will also be presented in a data listing for SAF.

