10.2 Laboratory Evaluations

10.2.1 Clinical Laboratory Evaluations

Subjects will be screened for HIV, hepatitis B surface antigen, antibody to hepatitis C virus and SARS-CoV-2. Results will be discussed with the subject. If a positive result occurs, the subject

will be referred for appropriate follow-up, and results will be reported as required by state law. These screening tests must be negative for the subject to be eligible to participate.

In order to be eligible for participation in the study and receipt of GRT-R910, the subject's clinical screening laboratory evaluations prior to each vaccination must be confirmed to meet the eligibility criteria as outlined in the Subject Inclusion Criteria (see [Section 7.1](#)).

The following tests will be performed by the local laboratory: WBC, Hb, PLT, ALT, AST, ALP, total bilirubin, CK, creatinine, PT/INR, aPTT, HIV serology, hepatitis B surface antigen, and hepatitis C antibody. Venous blood samples (approximately 17 mL) will be collected from each subject at the Screening Visit (Visit 00).

Clinical safety laboratory parameters evaluated after receipt of GRT-R910 will include WBC, Hb, PLT, ALT, AST, ALP, total bilirubin, CK, and creatinine.

Cardiac biomarker assessments will be performed for Cohorts 1 and 2 (subjects receiving booster dose) and Cohorts 3 and 4, and 6 to assess the potential risk of myocarditis with GRT-R910. Cardiac biomarker assessments include troponin T, C-reactive protein (CRP), and erythrocyte sedimentation rate (ESR).

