4.1.2. Repeat/unscheduled assessments

Additional exams may be scheduled as necessary to ensure the safety and well-being of subjects who experience AEs during the study. Any additional examinations during the study will be fully documented in the source documents and Unscheduled Visit eCRF.

Multiple visits within the same window will be dealt with for all populations as follows:

- In case the unscheduled visit was performed on or before the vaccination, so they can be considered to calculate the baseline value, the following rules will be applied:
 - If dates of visits (scheduled and/or unscheduled) are known and different, then the latest visit will be taken.
 - If date and time of visits are known and different, then the latest visit will be taken.
 - If dates of visits are the same, and time is not known, then latest visit based on SDTM sequence number will be taken.

- If data corresponding to an unscheduled visit met the baseline record selection criteria or when selecting the worst case in shift tables.
- If the unscheduled visit was performed after vaccination, the following rules will be applied:
 - If both scheduled and unscheduled visits fall within the same visit window, the scheduled visit will be used for analysis.
 - If one or multiple unscheduled visits occur within a single visit window without scheduled visit, no data will be used in the by-visit summaries of data analysis. If there are multiple unscheduled visits occur within a single visit window with ties, the later unscheduled visit will be used in the data listings.

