9.6. Electrocardiogram

Electrocardiogram (ECG) will be performed for Cohort 1 and 2 receiving booster dose only and Cohort 3, 4, and 6.

The ECG data will include heart rate and RR, PR, QT, and QRS durations. The investigator will be responsible for providing the interpretation of clinical significance for all ECG results.

The ECG assessments will be summarized as mean, SD, median, min, max, and mean of actual value and as mean, SD, median, min, and max of change from baseline. An interpretation by study days table in ECG will be summarized for the SAF

For subject with Early Termination (ET) visit, the ET visit will be set to the next protocol scheduled visit following ET within the specific study period. If the subjects completed all the scheduled visits and then discontinued, no mapping will be done.

All the ECG data will be listed.

10. Interim Analysis

No interim analysis was planned for this study; however, there may be unplanned interim analyses in light of the nature of Phase 1 study.

11. Changes in the Planned Analysis

- Efficacy analysis was added to the section 8.1
- Explained the occurrence of potential unplanned interim analyses in section 10.
- Calculation of solicited AE duration in section 9.1.2

12. References

1. ICH. Guidance for Industry (E9 Statistical Principles for Clinical Trials)
2. Gritstone bio, Inc. Clinical study protocol GO-009 Version 5.0 09 Feb 2023.
3. https://www.sas.com/en_us/home.html
4. Martin Bland Prof. of Health Statistics University of York, Detecting a single event

Gritstone bio, Inc.
GO-009

Statistical Analysis Plan, Version 5.0
Date Issued: 09UN2023

5. ICH. Guidance for Industry (Integrated Addendum to ICH E6(R1): Guideline for Good Clinical Practice E6(R2))
6. Clopper, C.J., and Pearson, E.S. (1934), "The Use of Confidence or Fiducial Limits Illustrated in the Case of the Binomial", *Biometrika* 26, 404-413
7. U.S. Department of Health and Human Services Food and Drug Administration Center for Biologics Evaluation and Research, "Toxicity Grading Scale for Healthy Adult and Adolescent Volunteers Enrolled in Preventive Vaccine Clinical Trials", 2007

Approved

Gritstone bio, Inc.
GO-009

Statistical Analysis Plan, Version 5.0
Date Issued: 09JUN2023

13. Appendices

Appendix 1

Table 6 Schedule of Study Procedures: Cohorts 1 and 2 – Subjects NOT receiving booster dose

Study Visit	V00	V01	V02	V03	V04	V05	V06	V07	V08	Unsch Visit	Early Term Visit

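### Unscheduled post-dose troponin, CRP, ESR and ECG results enter no cardiac results table, because SAP 9.4 and 9.6 lack the worst-case summary that SAP 9.2 and 9.3 provide

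*SAP*

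**What the plan says.** Protocol 10.2.1 gives the purpose of the cardiac biomarkers: "to assess the potential risk of myocarditis with GRT-R910". ECGs follow a parallel schedule.

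SAP 4.1.2 allows tests outside the schedule: "Additional exams may be scheduled as necessary to ensure the safety and well-being of subjects who experience AEs during the study". It then sets two rules for unscheduled visits after vaccination:
- Where a window holds a scheduled and an unscheduled visit, the analysis takes the scheduled one.
- "If one or multiple unscheduled visits occur within a single visit window without scheduled visit, no data will be used in the by-visit summaries".

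The only exceptions it names are baseline selection and the choice of the worst case in shift tables. That bullet is an incomplete sentence and sits among the pre-vaccination rules. It is read here as a general exception.

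For hematology and chemistry, SAP 9.2 uses the exception. The shift from baseline to the "worst-case post-vaccination, which will include unscheduled and repeated assessments, will also be presented". SAP 9.3 does the same for vital signs.

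SAP 9.4 ("An interpretation by study days table will be summarized for the SAF") and SAP 9.6 ("An interpretation by study days table in ECG will be summarized for the SAF") plan value and change-from-baseline statistics plus the by-day interpretation table, and nothing else in tabular form. Both sections also promise full listings.

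**The concern.** Troponin T and ECG are the planned measurements most directly tied to the myocarditis question, and myocarditis is not named among the PIMMC examples in Protocol 11.1.5 or SAP 9.1.1.4. A reader of the study report would naturally turn to the cardiac tables for an answer.

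A result obtained because a subject had symptoms is by nature unscheduled. If it is abnormal and the next scheduled test is normal, the subject appears normal at every visit in those tables. The same SAP does not accept this for routine laboratory tests or vital signs. Protocol 12.4.2 also asks for clinical laboratory data to be summarized as a maximum across the visits after vaccination, and Protocol 10.2.1 places the cardiac biomarkers among the clinical laboratory evaluations.

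**Working it through.** **1. The plan's own figure.** SAP 4.3 gives the chance of at least one event in 10 subjects at a true rate of 20%. The formula is 1 − (1 − p)^n = 1 − 0.8^10 = 1 − 0.1074 = 89.26%, which reproduces the stated 89%. The point does not depend on this figure. It is context: in cohorts of 10, the design's sensitivity is expressed in single events.

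**2. The rule traced through the sections.**

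| Domain | By-visit output | Worst case with unscheduled tests |
|---|---|---|
| Hematology, chemistry (SAP 9.2) | yes | yes |
| Vital signs (SAP 9.3) | yes | yes |
| Cardiac biomarkers (SAP 9.4; Tables 14.3.5.4.1 to 14.3.5.4.4) | yes | none stated |
| ECG (SAP 9.6; Tables 14.3.5.6.1 to 14.3.5.6.4) | yes | none stated |

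Only 14.3.5.4.1, 14.3.5.4.2, 14.3.5.6.1 and 14.3.5.6.2 are titled as by visit. For the other four, the by-visit layout is an inference: SAP Table 2 defines change from baseline at each post-baseline visit.

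**3. When scheduled cardiac tests occur** (Protocol Table 2; SAP Tables 7 and 8; doses on nominal days).

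| Dose | First scheduled cardiac test | Days after dose | Days with no scheduled cardiac test before it |
|---|---|---|---|
| Prime, Day 1 | Day 8 (+2d) | 8 − 1 = 7, up to 9 | Days 2 to 7: 6 |
| Boost, Cohorts 1 and 2, Day 113 | Day 120 (+2d) | 120 − 113 = 7, up to 9 | Days 114 to 119: 6 |
| Boost, Cohorts 3, 4 and 6, Day 29 | Day 37 (+2d) | 37 − 29 = 8, up to 10 | Days 30 to 36: 7 |

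The two contacts in each of these gaps are phone, text or e-mail. In Cohorts 3, 4 and 6 the Day 29 test precedes the boost, so it is not a post-boost result.

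Over the 28 days after the prime (Days 2 to 29), scheduled windows cover Days 8 to 10 and 26 to 29, which is 3 + 4 = 7 of 28 days. After the boost they cover 6 of 28: Days 120 to 122 and 139 to 141 in Cohorts 1 and 2, and Days 37 to 39 and 55 to 57 in Cohorts 3, 4 and 6.

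**4. What happens to an early test.** A troponin on Day 3 falls in the V02 window (Day 2 +1d). If the phone contact took place in that window, the scheduled visit is used, and it has no troponin. If it did not, no data are used. A test on Day 7 falls in no window and has no column. In each case the result reaches no cardiac results table.

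**5. Illustration of size.** Assume one subject whose only abnormal cardiac result is unscheduled. Exact (Clopper-Pearson) 95% limits:
- 0/10: upper limit 1 − 0.025^(1/10) = 30.8%, so 0 to 30.8%.
- 1/10: lower limit 1 − 0.975^(1/10) = 0.3%; the upper limit solves P(X ≤ 1) = 0.025, giving 44.5%.
- If all 50 subjects had cardiac data: 0/50 gives 0 to 7.1%; 1/50 gives 0.1 to 10.6%.

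In Cohorts 1 and 2 only subjects who receive the booster have these tests, so denominators there may be below 10.

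**The case against.** The strongest reply is that the patient is not lost. A reader might infer that a myocarditis case could be missing from every summary table. The documents do not support that. A symptomatic episode within 28 days of a dose is an unsolicited AE (SAP 9.1.1). An unscheduled visit to medical personnel meets the MAAE definition (Protocol 11.1.5). An abnormal laboratory finding can itself be an AE (Protocol 11.1.1). A serious event goes to the SAE tables, and a related SAE within 28 days is a halting criterion (Protocol 11.6.1). All of this stands. What remains is the test result itself, which AE tables do not display, and abnormal results that nobody reports as an AE.

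Second, the ECG and biomarker rows are blank in the Unscheduled column of the schedules, while safety labs and vital signs are marked there. That may explain why only SAP 9.2 and 9.3 mention unscheduled tests. It makes such data less expected but not excluded, since SAP 4.1.2 permits additional exams.

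Third, it would be too strong to say that only scheduled visits count. Early termination results are mapped to the next scheduled visit, and pre-dose unscheduled results can serve as baseline.

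Fourth, no confidence intervals are planned for these tables, cardiac tests are not a listed primary outcome, and all results are listed. These facts limit the importance of the point. A listing alone, however, was not thought sufficient for routine laboratory tests.

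Finally, the support from Protocol 12.4.2 is partial. It covers the biomarkers by their placement in 10.2.1, does not mention unscheduled tests, and does not extend to ECG.

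**Conclusion.** The gap is real and narrow. As written, an unscheduled post-dose troponin T, CRP, ESR or ECG result enters no cardiac results table, and in the 6 to 7 days before the first scheduled test after each dose every such result is unscheduled. The consequence is incomplete display of test results. It is not loss of the clinical event, and no planned analysis becomes invalid.

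The 0/10 against 1/10 contrast shows what one omitted result does to a cohort display. It assumes the event and does not predict it, and the intervals would not appear in the planned tables.

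The conclusion rests on three assumptions: doses on their nominal days; a by-visit layout for the value and change tables; and no worst-case row in table shells that are not part of the documents. It is a worthwhile, low-cost improvement.

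**What to change.** In SAP 9.4 and 9.6, add a worst-case post-vaccination interpretation for each dose, including unscheduled and repeat assessments. Use the categories already in SAP Table 2: normal, abnormal not clinically significant, abnormal clinically significant. The wording of SAP 9.2 cannot be copied unchanged, because it concerns toxicity grades and none are defined for cardiac tests.

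- Add the row to Tables 14.3.5.4.1, 14.3.5.4.2, 14.3.5.6.1 and 14.3.5.6.2.
- Add the maximum post-dose biomarker value, at least for troponin T, to Tables 14.3.5.4.3 and 14.3.5.4.4.
- State that a test taken on the boost day before injection belongs to the prime period.
- Label the row as including unscheduled tests, since these are prompted by symptoms and are not comparable with the scheduled columns.

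The cost is a sentence in each section and minor programming. No extra tests or data are needed, and no sample size or other planned analysis changes.
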